 - creatinine $\leq 1.5 \times$ ULN
OR

- creatinine clearance ≥ 50 mL/min/1.73 m² for participants with creatinine levels above institutional normal (using the Cockcroft-Gault Formula below):

$$\text{Female CrCl} = \frac{(140 - \text{age in years}) \times \text{weight in kg} \times 0.85}{72 \times \text{serum creatinine in mg/dL}}$$

$$\text{Male CrCl} = \frac{(140 - \text{age in years}) \times \text{weight in kg}}{72 \times \text{serum creatinine in mg/dL}}$$

- 3.1.7 The effects of eribulin and pembrolizumab on the developing human fetus are unknown. For this reason, women of child-bearing potential (WOCBP) and men must agree to use adequate contraception (hormonal or barrier method of birth control; abstinence) prior to study entry and for the duration of study participation. A male participant must agree to use a contraception as detailed in Appendix G of this protocol during the treatment period and for at least 20 weeks, corresponding to the time needed to eliminate any study treatments, plus an additional 120 days (a spermatogenesis cycle) after the last dose of study treatment. A female participant is eligible to participate if she is not pregnant (see Appendix G), not breastfeeding, and at least one of the following conditions applies:

- a.) Not a woman of childbearing potential (WOCBP) as defined in Appendix G
- OR
- b.) A WOCBP who agrees to follow the contraceptive guidance in Appendix G during the treatment period and for at least 20 weeks plus an additional 30 days (a menstruation cycle) after the last dose of study treatment.

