WOCBP should use an adequate method to avoid pregnancy for at least 20 weeks plus an additional 30 days after the last dose of investigational drug. Women of childbearing potential must have a negative serum pregnancy test within 72 hours prior to the start of Eribulin and Pembrolizumab. Women must not be breastfeeding. Women who are not of childbearing potential (*i.e.*, who are postmenopausal or surgically sterile) do not require contraception. Women of childbearing potential (WOCBP) is defined as any female who has experienced menarche and who has not undergone surgical sterilization (hysterectomy or bilateral oophorectomy) or who is not postmenopausal. Menopause is defined clinically as 12 months of amenorrhea in a woman over 45 in the absence of other biological or physiological causes. In addition, women under the age of 55 must have a documented serum follicle stimulating hormone (FSH) level less than 40 mIU/mL.

- 3.1.8 Ability to understand and the willingness to sign a written informed consent document.

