4. REGISTRATION PROCEDURES

4.1 General Guidelines for DF/HCC Institutions

Institutions will register eligible participants in the Clinical Trials Management System (CTMS) OnCore. Registrations must occur prior to the initiation of protocol therapy. Any participant not registered to the protocol before protocol therapy begins will be considered ineligible and registration will be denied.

An investigator will confirm eligibility criteria and a member of the study team will complete the protocol-specific eligibility checklist.

Following registration, participants may begin protocol therapy. Issues that would cause treatment delays should be discussed with the Overall PI. If a participant does not receive protocol therapy following registration, the participant's registration on the study must be canceled. Registration cancellations must be made in OnCore as soon as possible.

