22. APPENDIX G: CONTRACEPTIVE GUIDANCE AND PREGNANCY TESTING

Woman of Childbearing Potential (WOCBP)

A woman is considered fertile following menarche and until becoming post-menopausal unless permanently sterile (see below)

Women in the following categories are not considered WOCBP:

- Premenarchal
- Premenopausal female with 1 of the following:
 - Documented hysterectomy
 - Documented bilateral salpingectomy
 - Documented bilateral oophorectomy

Note: Documentation can come from the site personnel's review of the participant's medical records, medical examination, or medical history interview.

- Postmenopausal female
 - A postmenopausal state is defined as no menses for 12 months without an alternative medical cause.
 - A high follicle stimulating hormone (FSH) level in the postmenopausal range may be used to confirm a postmenopausal state in women not using hormonal contraception or hormonal replacement therapy (HRT). However, in the absence of 12 months of amenorrhea, confirmation with two FSH measurements in the postmenopausal range is required.
 - Females on HRT and whose menopausal status is in doubt will be required to use one of the non-hormonal highly effective contraception methods if they wish to continue their HRT during the study. Otherwise, they must discontinue HRT to allow confirmation of postmenopausal status before study enrollment.

Contraception Requirements

Male Participants:

Male participants with female partners of childbearing potential are eligible to participate if they agree to one of the following during the protocol defined time frame in section 3.1.10:

- Be abstinent from penile-vaginal intercourse as their usual and preferred lifestyle (abstinent on a long term and persistent basis) and agree to remain abstinent
- Use a male condom plus partner use of a contraceptive method with a failure rate of <1% per year as described in Table 12 when having penile-vaginal intercourse with a woman of childbearing potential who is not currently pregnant.
 - Note: Men with a pregnant or breastfeeding partner must agree to remain abstinent from penile-vaginal intercourse or use a male condom during each episode of penile penetration.

Female Participants:

Female participants of childbearing potential are eligible to participate if they agree to use a highly effective method of contraception consistently and correctly as described in Table 12 during the protocol-defined time frame in Section 3.1.10.

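### Section 3.1.7 reverses the FSH condition for menopause in women under 55 and so conflicts with Appendix G

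*Combined protocol and SAP*

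**What the plan says.** Section 3.1.7 deals with childbearing potential in two places.

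Condition (a) admits a woman who is "Not a woman of childbearing potential (WOCBP) as defined in Appendix G". So the appendix is named as the source of the definition.

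The paragraph after the two conditions then gives a definition of its own: "Menopause is defined clinically as 12 months of amenorrhea in a woman over 45 in the absence of other biological or physiological causes". The next sentence opens as an addition to this and says that "women under the age of 55 must have a documented serum follicle stimulating hormone (FSH) level less than 40 mIU/mL". The same paragraph releases women who are not of childbearing potential from contraception, and for the others it says: "Women of childbearing potential must have a negative serum pregnancy test within 72 hours prior to the start of Eribulin and Pembrolizumab".

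Appendix G states: "A postmenopausal state is defined as no menses for 12 months without an alternative medical cause". On the hormone it says: "A high follicle stimulating hormone (FSH) level in the postmenopausal range may be used to confirm a postmenopausal state in women"; the sentence goes on to limit this to women taking neither hormonal contraception nor HRT. It adds that "in the absence of 12 months of amenorrhea, confirmation with two FSH measurements in the postmenopausal range is required". A further bullet covers women on HRT whose menopausal status is in doubt. To stay on HRT they must use a non-hormonal highly effective method; otherwise they stop HRT so that their status can be confirmed before enrollment. Appendix G gives no numerical FSH cut-off.

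**The concern.** The FSH sentence in 3.1.7 is meant to make the menopause definition stricter for younger women, for whom amenorrhea alone is less convincing. With the inequality pointing down, it does the reverse of a confirmation. A low value passes and a high value fails, while Appendix G reads a high value as the evidence for menopause. The words are spelled out, so this is not a symbol lost in reading the PDF, and the text is in the current eligibility section.

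WOCBP status decides two things: whether contraception is required during treatment and for 20 weeks plus 30 days afterwards, and whether the serum pregnancy test within 72 hours before the first dose is required. Section 2.5.2.5 reports fetal anomalies in rats given eribulin, so the rule should be right. Under Section 4.1, "a member of the study team will complete the protocol-specific eligibility checklist". A person who does so from 3.1.7 has two rules that disagree within one criterion, and nothing says which prevails.

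**Working it through.** No calculated figure is involved, so the check sets the two definitions side by side.

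**Inputs**

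- Section 3.1.7: 12 months of amenorrhea, age over 45, no other cause, and under age 55 also FSH below 40 mIU/mL. The FSH condition is worded as a *must*.
- Appendix G: 12 months without menses and no alternative medical cause. FSH *may* be used to confirm, and the confirming direction is high. A separate rule covers HRT.

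**Who is touched.** The FSH sentence can change the status only of women who meet the rest of the 3.1.7 definition and are under 55. In completed years, that is amenorrheic women aged 46 to 54 with no other cause.

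**Classification of those women**

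| Group | 3.1.7 as written | 3.1.7 with only the sign reversed | Appendix G |
|---|---|---|---|
| No HRT, FSH below 40 | Menopausal | WOCBP | Postmenopausal, on amenorrhea alone |
| No HRT, FSH 40 or above | WOCBP | Menopausal | Postmenopausal |
| On HRT, status in doubt, FSH below 40 | Menopausal, no contraception | WOCBP | Non-hormonal contraception, or stop HRT and confirm |
| On HRT, status in doubt, FSH 40 or above | WOCBP | Menopausal, no contraception | Non-hormonal contraception, or stop HRT and confirm |

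**Reading the table**

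1. *Direction.* In the first two rows, 3.1.7 as written accepts the group with the lower FSH and rejects the group with the higher FSH. Appendix G associates high values with menopause. The direction is therefore wrong by the protocol's own text.
2. *Mismatch without HRT.* As written, the two definitions disagree in 1 of these 2 groups (FSH 40 or above), and there 3.1.7 is the more cautious. With only the sign reversed they still disagree in 1 of 2, now the group below 40. The sign decides which group is mismatched. A mismatch exists at all because 3.1.7 requires an FSH result that Appendix G leaves optional once 12 months of amenorrhea are present.
3. *Mismatch with HRT.* In the third row, 3.1.7 as written could release a woman whom Appendix G does not. This assumes that she is treated as meeting the 12-month amenorrhea condition while on HRT. Reversing the sign moves this gap to the fourth row, because 3.1.7 has no HRT rule.

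**Number of women.** The accrual table in Section 13.2 plans for 28 women among 57 participants. The documents give no distribution of age, FSH or HRT use, so no count can be derived for any row.

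**The case against.** The strongest reply is that condition (a) sends the reader to Appendix G, whose direction is right, so the stray sentence in 3.1.7 may do little. Other safeguards remain: the amenorrhea and age conditions, a pregnancy test among the baseline assessments in Section 10 (the calendar text does not limit it to WOCBP; the table is not shown), and repeat testing under Appendix G when a period is missed or pregnancy is suspected. This stands as a reason to call the effect small. It does not remove the conflict, because the same criterion goes on to state its own mandatory definition.

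A second reply is that the disagreement comes from FSH being mandatory in one place and optional in the other, not from the sign. That is partly right, as the sign-reversed column shows. The reversed direction is still an error in itself: a confirmatory check that passes the unconfirmed and fails the confirmed is wrong whatever Appendix G says about its necessity.

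Some stronger readings are tempting, and the documents do not support them:

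- A reader might infer that the reversed sign frees many women from contraception whom Appendix G would hold to it. Outside the HRT case, amenorrheic women aged 46 to 54 with FSH below 40 are postmenopausal under Appendix G too.
- A reader might infer the opposite, that 3.1.7 exempts nobody beyond Appendix G. The HRT bullet rules out so flat a statement.
- A reader might take 40 mIU/mL as the established boundary of the postmenopausal range. Only 3.1.7 gives that number, so the documents support the direction error and not the cut-off.
- A reader might assume that the eligibility checklist repeats the error. The checklist is not among the documents.

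**Conclusion.** The point holds as a drafting error in an operative eligibility rule, of minor weight. Section 3.1.7 states the FSH condition in the wrong direction relative to Appendix G, and the two definitions conflict for amenorrheic women aged 46 to 54 with FSH of 40 mIU/mL or above. Two further differences lie beside it and would survive a change of sign: FSH is mandatory in 3.1.7 and optional in Appendix G, and only Appendix G has a rule for women on HRT whose status is in doubt.

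This rests on reading the FSH sentence as an added condition for counting as menopausal. Its position directly after the menopause definition supports that reading. The alternative, a low-FSH entry requirement for every woman under 55, would have no stated reason. The 12-week primary endpoint, the power of each cohort and the planned analyses are unaffected.

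**What to change.** Either of two edits is enough.

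- **Correct the sentence.** In 3.1.7, replace the FSH wording with 40 mIU/mL or above (postmenopausal range). Add a sentence saying which definition governs when 3.1.7 and Appendix G differ, and keep Appendix G's HRT rule in force. Reversing the sign without the governing sentence would only move the mismatch to women below 40. The sponsor should confirm the cut-off, since Appendix G offers none.
- **Delete the sentence.** Remove the FSH condition from 3.1.7 and rely on Appendix G alone. This also removes the mandatory test, and it leaves the HRT rule as it is.

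Appendix G need not be rewritten to require FSH. If the eligibility checklist carries the same wording, correct it in the same amendment.

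The cost is one or two sentences and, if needed, one checklist line. If enrollment has ended, which the documents do not say, the change serves mainly to set the record right.

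### Section 3.1.7 inverts the FSH test for menopause in women under 55, contradicting Appendix G, to which the same criterion defers

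*Combined protocol and SAP*

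**What the plan says.** Section 3.1.7 handles childbearing potential in two places. Condition (a) admits a woman who is "Not a woman of childbearing potential (WOCBP) as defined in Appendix G". Later text in the same criterion gives its own definition: menopause is "12 months of amenorrhea in a woman over 45 in the absence of other biological or physiological causes", and in addition "women under the age of 55 must have a documented serum follicle stimulating hormone (FSH) level less than 40 mIU/mL".

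The classification has two consequences in 3.1.7. Women "who are postmenopausal or surgically sterile) do not require contraception". The pregnancy test close to dosing is tied to the other group: "Women of childbearing potential must have a negative serum pregnancy test within 72 hours prior to the start of Eribulin and Pembrolizumab".

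Appendix G defines the postmenopausal state as "no menses for 12 months without an alternative medical cause", with no age limit and no compulsory FSH. It mentions FSH twice, both times in the high direction: "A high follicle stimulating hormone (FSH) level in the postmenopausal range may be used to confirm a postmenopausal state", and "in the absence of 12 months of amenorrhea, confirmation with two FSH measurements in the postmenopausal range is required". It gives no numerical cut-off.

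**The concern.** The FSH line is the one extra check that 3.1.7 places on women under 55 before they are treated as postmenopausal. Judged by Appendix G, it points the wrong way: a low value lets a woman through and a high value stops her. The direction is written in words, so it is not a symbol lost in text extraction, and it stands in current eligibility text.

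Two things are at stake. First, a woman whose amenorrhea is not menopausal and whose FSH is low meets no obstacle at this check. She is then outside the contraception requirement and the 72-hour serum test, while receiving a drug that Section 2.5.2.5 describes as teratogenic in rats. Second, site staff applying one criterion can reach two answers for the same woman.

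**Working it through.** The plan gives no figure to reproduce, so the check sets the two texts side by side.

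**Inputs.** From 3.1.7: age over 45, 12 months' amenorrhea, no other cause, and FSH below 40 mIU/mL if under 55. From Appendix G: 12 months without menses and no alternative cause, with FSH optional once those 12 months are met.

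**Who is covered.** Over 45 and under 55 is 46 to 54 in whole years.

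**Illustrative values.** FSH of 10 and of 80 mIU/mL stand for either side of 40. Because Appendix G has no cut-off, treating 40 as the lower edge of the postmenopausal range is an assumption. The classifications below do not depend on it, because Appendix G accepts 12 months' amenorrhea by itself.

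For a woman aged 46 to 54 with 12 months' amenorrhea and no other cause:

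| Text of 3.1.7 | FSH | Under 3.1.7 | Under Appendix G | Result |
|---|---|---|---|---|
| As written (below 40) | 10 | postmenopausal | postmenopausal | agree |
| As written (below 40) | 80 | WOCBP | postmenopausal | conflict |
| Threshold reversed, Appendix G unchanged | 10 | WOCBP | postmenopausal | conflict |
| Threshold reversed, Appendix G unchanged | 80 | postmenopausal | postmenopausal | agree |
| Duplicate definition deleted | 10 or 80 | none stated | postmenopausal | single answer |

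Three results follow.

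1. As written, the FSH check changes the classification only of the high-FSH woman, whose result Appendix G would read as confirming menopause. It never stops the low-FSH woman.
2. Reversing the threshold alone makes the check work but moves the conflict to low-FSH women. That is why the text must also say which definition governs.
3. Deleting the duplicate removes the conflict but leaves no compulsory FSH check after 12 months' amenorrhea.

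**Contraception period at stake.** For a female participant it is the treatment period plus 20 weeks and 30 days after the last dose: 20 × 7 = 140 days, and 140 + 30 = 170 days.

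**The case against.** The strongest reply is that the operative test already points to the right text. Condition (a) of 3.1.7 relies on Appendix G, and Appendix G has FSH in the correct direction. On the table above, the inverted line exempts nobody whom Appendix G would have kept as a WOCBP, and its one direct effect, retaining high-FSH women as WOCBP, is cautious. This stands. A reader might infer that the error opens a new route around contraception. The documents do not support that, because the low-FSH woman is exempt under Appendix G on amenorrhea alone.

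Other protections also count. Both definitions exclude amenorrhea with another cause. Section 3.1.7 requires every female participant not to be pregnant. Section 10 lists a baseline pregnancy test without limiting it to WOCBP, although within 14 days rather than 72 hours. Appendix G adds testing when pregnancy is suspected, at scheduled time points and as locally required. The calendar grid is not readable in the available text, so what it schedules cannot be judged. Appendix G's missed-cycle trigger does not help a woman who expects no cycles.

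None of this makes the sentence right. Read as a stand-alone requirement on all women under 55, it would exclude women for high FSH, which Appendix G nowhere does. Read as describing WOCBP, it no longer fits the menopause definition that it extends.

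**Conclusion.** The point holds as an inverted threshold in an operative eligibility criterion, together with two conflicting definitions inside that criterion. The harm is a safeguard that cannot work, not a new exemption. Sample size, endpoints and analysis are unaffected.

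The number of women affected cannot be derived from the documents and may be zero. A reader might take the 28 women in Table 10 as an upper limit, but those are accrual targets and nothing caps enrolment by sex.

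Three further inferences should be avoided:

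- Reversing the threshold does not reconcile the two texts in full. The age limit over 45 appears only in 3.1.7. Appendix G accepts bilateral salpingectomy, which 3.1.7 does not list. Appendix G also allows two FSH values in place of 12 months' amenorrhea.
- The documents do not show that the eligibility checklist repeats the error. Section 4.1 mentions the checklist but does not reproduce it.
- The error does not by itself require a compulsory FSH of 40 or higher in Appendix G, which makes FSH optional after 12 months' amenorrhea.

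The conclusion that the direction is wrong rests on Appendix G's own use of FSH and needs no outside source.

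**What to change.** Take one of two routes.

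- **Keep the check.** In 3.1.7, replace the requirement for FSH below 40 mIU/mL with 40 mIU/mL or higher (postmenopausal range), and state whether 3.1.7 or Appendix G governs where they differ.
- **Drop the duplicate.** Delete the menopause and WOCBP definition from the later text of 3.1.7 and rely on Appendix G alone. This also removes the remaining differences in age, salpingectomy and the two-FSH route.

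Correct the eligibility checklist only if it repeats the line. Recheck any woman aged 46 to 54 who was classed as postmenopausal using the FSH line and is still on treatment or within 170 days of her last dose. There may be none, since Section 5.6 ends long-term follow-up with Version 15MAY2024.

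The cost is one or two sentences and a short chart check. Under the first route, if 3.1.7 governs, a few low-FSH women would need contraception and the 72-hour pregnancy test. Under the second, the extra check for women under 55 is given up, which should be a deliberate choice.

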3.2 Exclusion Criteria

- 3.2.1 Participants who have had standard chemotherapy or radiotherapy within 3 weeks prior to entering the study.
- 3.2.2 Participants who have not recovered from adverse events (grade 2 or higher toxicities) due to agents administered, radiotherapy, or surgery, with the exception of alopecia and anemia.
- 3.2.3 Previous treatment with eribulin or any anti-PD-1, PD-L1, or PD-L2 agent, or with an agent directed to another stimulatory or co-inhibitory T-cell receptor (eg, CTLA-4, OX-40, CD137).
- 3.2.4 Participants who are currently participating in or have participated in a study of an investigational agent or have used an investigational device within 3 weeks prior to the first dose of study treatment.
Note: Participants who have entered the follow-up phase of an investigational study may participate as long as it has been 3 weeks after the last dose of the previous investigational agent.
- 3.2.5 Known brain metastases that are untreated, symptomatic or require therapy to control symptoms. Participants with previously diagnosed brain metastases are eligible if they have completed treatment at least 4 weeks prior to registration, are neurologically stable and have not experienced any new neurologic symptoms for the last 4 weeks prior to study entry, and have recovered from the effects of radiotherapy or surgery. There must also be no requirement for immunosuppressive doses of systemic corticosteroids (>10 mg/day prednisone equivalents) for at least 2 weeks prior to study drug administration. Treatment for brain metastases may have included whole brain radiotherapy, radiosurgery, surgery, or a combination as deemed appropriate by the treating physician.
- 3.2.6 Have received a live vaccine within 30 days prior to the first dose of study drug. Examples of live vaccines include, but are not limited to, the following: measles, mumps, rubella, varicella/zoster (chicken pox), yellow fever, rabies, Bacillus Calmette–Guérin (BCG), and typhoid vaccine. Seasonal influenza vaccines for injection are generally killed virus vaccines and are allowed; however, intranasal influenza vaccines (eg, FluMist®) are live attenuated vaccines and are not allowed.
- 3.2.7 Inability to comply with study and/or follow-up procedures.
- 3.2.8 History of severe hypersensitivity reaction (\geq Grade 3) to any monoclonal antibody.
- 3.2.9 History of allergic reactions attributed to compounds of similar chemical or biologic composition to Eribulin or Pembrolizumab.

- 3.2.10 Uncontrolled intercurrent illness including, but not limited to, ongoing or active infection, symptomatic congestive heart failure, unstable angina pectoris, cardiac arrhythmia, or psychiatric illness/social situations which in the PI's opinion makes it undesirable for the participant to participate in the trial or which would jeopardize compliance with the trial and study requirements.
- 3.2.11 Pregnant women (WOCBP who had a positive serum pregnancy test on screening or 72 hours prior to initiation of study protocol) are excluded from this study because the effects of Eribulin and Pembrolizumab on the developing fetus are unknown. There is the potential for teratogenic or abortifacient effects. Because there is an unknown but potential risk for adverse events in nursing infants secondary to treatment of the mother with Eribulin and Pembrolizumab, breastfeeding should be discontinued if the mother is treated with Eribulin and Pembrolizumab.
- 3.2.12 Because the effects of pembrolizumab on chronic viral infection are not well known, participants should be excluded if they have known history of testing positive for human immunodeficiency virus (HIV) (true positive) or known acquired immunodeficiency syndrome (AIDS) or if they have a positive test for hepatitis B virus surface antigen (HBV sAg) or hepatitis C virus ribonucleic acid (HCV antibody) indicating acute or chronic infection.
- 3.2.13 Participants with active autoimmune disease or history of autoimmune disease that might recur, which may affect vital organ function or require immune suppressive treatment including systemic corticosteroids, are excluded. These include but are not limited to participants with a history of immune related neurologic disease such as multiple sclerosis, autoimmune (demyelinating) neuropathy, Guillain-Barre syndrome, or myasthenia gravis; participants with a history of systemic autoimmune disease such as SLE, connective tissue diseases, scleroderma, inflammatory bowel disease (IBD), Crohn's, ulcerative colitis, or hepatitis; and participants with a history of toxic epidermal necrolysis (TEN), Stevens-Johnson syndrome, or phospholipid syndrome. These participants should be excluded because of the risk of recurrence or exacerbation of disease. Participants with vitiligo or endocrine deficiencies, including thyroiditis managed with replacement hormones such as physiologic corticosteroids, are eligible. Participants with rheumatoid arthritis or other arthropathies; Sjögren's syndrome; psoriasis controlled with topical medication; or participants with positive serology, such as antinuclear antibodies (ANA) or anti-thyroid antibodies, should be evaluated for the presence of target organ involvement and potential need for systemic treatment but should otherwise be eligible.
- 3.2.14 Participants are permitted to enroll if they have vitiligo, type I diabetes mellitus, residual hypothyroidism due to autoimmune condition only requiring hormone replacement, psoriasis not requiring systemic treatment, or conditions not expected to recur in the absence of an external trigger (precipitating event).

- 3.2.15 Participants should be excluded if they have a condition requiring systemic treatment with either corticosteroids (>10 mg daily prednisone equivalents) or other immunosuppressive medications within 14 days of study drug administration. Inhaled or topical steroids and adrenal replacement doses <10 mg daily prednisone equivalents are permitted in the absence of active autoimmune disease. Participants are permitted to use topical, ocular, intraarticular, intranasal, and inhalational corticosteroids (with minimal systemic absorption). Physiologic replacement doses of systemic corticosteroids are permitted, even if <10 mg/day prednisone equivalents. A brief course of corticosteroids for prophylaxis (e.g., contrast dye allergy) or for treatment of non-autoimmune conditions (e.g., delayed-type hypersensitivity reaction caused by contact allergen) is permitted.
- 3.2.16 Participants with a history of pneumonitis or interstitial lung disease.
- 3.2.17 History of primary immunodeficiency or solid organ transplantation.
- 3.2.18 Participants who have had evidence of active or acute diverticulitis, intra-abdominal abscess, GI obstruction, or fistula or abdominal carcinomatosis (which are known risk factors for bowel perforation) should be evaluated for the potential need for additional treatment before coming on study.

